- MK-4482-001 Part 1: A total of 218 hospitalized participants with COVID-19 received at • least 1 dose of MOV (72 participants received MOV 800 mg) and 75 participants received placebo. The overall safety profiles observed in P001 were generally comparable for MOV doses and placebo. No trends in AEs or changes in clinical laboratory values were observed as a function of dose or study intervention. The most frequently reported AEs (≥5%) in any MOV group were COVID-19, AST/ALT elevations, constipation, bacterial pneumonia, hyperglycemia, and respiratory failure. The most frequently reported AEs (\geq 5%) in the placebo group were constipation, COVID-19, COVID-19 pneumonia, ALT increased, and respiratory failure. SAEs were reported for 15.4% participants (15.1% participants in the MOV groups combined and 16.0% in the placebo group). One drug-related (as per investigator) SAE (Grade 3 urticaria) was reported for 1 participant (MOV 200 mg). A total of 16 participants had AEs leading to death (6.4% in the MOV groups combined and 2.7% in the placebo group). Most deaths occurred in participants who had severe COVID-19 at baseline (12 of 16), were >60 years of age (13 of 16), had underlying comorbidities (14 of 16), and/or had duration of COVID-19 symptoms >5 days before randomization (12 of 16). None of the deaths were considered drug-related per investigator assessment. The study was stopped due to lack

of clinical benefit in this population (participants already hospitalized prior to randomization) and did not proceed to Part 2.

- MK-4482-002 Part 1: A total of 225 nonhospitalized participants with COVID-19 received at least 1 dose of MOV (74 received at least 1 dose of MOV 800 mg) and 74 participants received placebo in the APaT population. The safety profiles for MOV (all doses) and placebo were comparable. No trends in AEs or changes in clinical laboratory values were observed as a function of dose or study intervention. The most frequently reported AEs (≥5%) were COVID-19 pneumonia in any MOV group and diarrhea and COVID-19 in the placebo group. The percentage of participants with drug-related AEs per the investigator was comparable across all intervention groups. SAEs were reported for 3.6% participants in the MOV combined group and for 5.4% participants in the placebo group. No SAEs were considered drug-related per investigator. Efficacy data are summarized in Section 4.3.1.

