8.4.6 Disease-related Events and/or Disease-related Outcomes Not Qualifying as AEs or SAEs

Certain efficacy endpoints including hospitalizations and mortality must be collected throughout the study (ie, during both treatment and follow-up periods). From the time of randomization through 14 days after cessation of study intervention, these events must be reported as described in Section 8.4.1. New hospitalizations and/or deaths that occur after 14 days after cessation of treatment must continue to be assessed for seriousness and causality. However, they must only be reported to the Sponsor within 24 hours as new SAEs if there is evidence to suggest a causal relationship between the study intervention and the SAE.

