9.1 Statistical Analysis Plan Summary

Key elements of the statistical analysis plan are summarized below; the comprehensive plan is provided in Section 9.2 to Section 9.12.

Study Design Overview	A Phase 3, Multicenter, Randomized, Double-blind, Placebo- controlled Study to Evaluate the Efficacy and Safety of MK-4482 for the Prevention of COVID-19 (Laboratory-confirmed SARS- CoV-2 Infection With Symptoms) in Adults Residing With a Person With COVID-19.		
Treatment Assignment	 Approximately 1376 participants (regardless of SARS-CoV-2 results in baseline NP swabs) will be randomized in a 1:1 ratio (stratified per Section 6.3.2) to receive either MOV or placebo, Q12H for 5 days. MOV 800 mg (n~688) Placebo (n~688) 		
Analysis Populations	Efficacy: mITT Safety: APaT		
Primary Endpoint(s)	Efficacy: Percentage of participants with undetectable SARS-CoV-2 in baseline NP swabs developing COVID-19 through Day 14. Safety: AEs, and AEs leading to discontinuation of study intervention.		
Secondary Endpoints	 Percentage of participants (regardless of SARS-CoV-2 results in baseline NP swabs) developing COVID-19 through Day 14 Percentage of participants with undetectable SARS-CoV-2 in baseline NP swabs developing COVID-19 through Day 29. Percentage of participants with undetectable SARS-CoV-2 in baseline NP swabs having viral transmission through Day 14. Percentage of participants with detectable SARS-CoV-2 in baseline NP swabs having viral transmission through Day 14. Percentage of participants with detectable SARS-CoV-2 in baseline NP swabs developing COVID-19 through Day 14. 		
Statistical Methods for Key Efficacy Analyses			
Statistical Methods for Key Safety Analyses			

x / • • •	
Interim Analyses	One IA will be performed to evaluate safety and futility with respect to the primary efficacy hypothesis. Results will be reviewed by an eDMC. A summary of the IA is provided below. Further details are provided in Section 9.7.
	• Timing: To be conducted when approximately 55% of the participants with undetectable SARS-CoV-2 in baseline NP swabs have either completed the Day 14 visit or discontinued from the study prior to the Day 14 visit.
	• Testing: The primary efficacy hypothesis will be tested.
Multiplicity	A gatekeeping strategy will be used to control the overall FWER associated with the primary and secondary analyses.
	The following efficacy hypotheses will be tested sequentially at a one-sided 2.49% Type I error rate at final analyses:

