9.6.2 Statistical Methods for Safety Analyses

Safety and tolerability will be assessed by clinical review of all relevant parameters including AEs and laboratory tests.

The analysis of safety results for participants will follow a tiered approach (Table 6). The tiers differ with respect to the analyses that will be performed. Adverse events (specific terms as well as system organ class terms) and events that meet PDLCs in laboratory will be classified as belonging to "Tier 2" or "Tier 3" based on the number of events observed.

Safety parameters or adverse events of special interest that are identified a priori constitute "Tier 1" safety endpoints that will be subject to inferential testing for statistical significance. No a priori clinical events of concern have been identified for this study.

Tier 2 parameters will be assessed via point estimates with 95% confidence intervals provided for differences in the percentage of participants with events (via the unstratified Miettinen and Nurminen method (1985) [Miettinen, O. and Nurminen, M. 1985]).

Because many 95% confidence intervals for Tier 2 events may be provided without adjustment for multiplicity, the confidence intervals should be regarded as a helpful descriptive measure to be used in review, not a formal method for assessing the statistical significance of the between-group differences in adverse events and safety parameters that meet predefined limits of change.

ECIs identified in Section 8.4.7 are considered Tier 2 events, as well as the broad AE categories consisting of the percentage of participants with any AE, a drug-related AE, a serious AE, an AE, which is both drug-related and serious, and discontinuation due to an AE will be considered Tier 2 endpoints. In addition, individual AEs observed in $\geq 1\%$ of participants in any intervention group will be categorized as a Tier 2 event. Events reported less frequently than in 1% of participants would obscure the assessment of the overall safety profile and add little to the interpretation of potentially meaningful differences.

Safety endpoints that are not Tier 2 events are considered Tier 3 events. Only point estimates by treatment group are provided for Tier 3 safety parameters.

Continuous Safety Measures

For continuous measures such as changes from baseline in laboratory parameters, summary statistics for baseline, on-treatment, and change from baseline values will be provided by treatment group in Table format.

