10.3.1 Definition of AE

AE definition

- An AE is any untoward medical occurrence in a clinical study participant, temporally associated with the use of study intervention, whether or not considered related to the study intervention.
- Note: An AE can therefore be any unfavorable and unintended sign (including an abnormal laboratory finding), symptom, or disease (new or exacerbated) temporally associated with the use of a study intervention.
- Note: For purposes of AE definition, study intervention (also referred to as Sponsor's product) includes any pharmaceutical product, biological product, vaccine, diagnostic agent, medical device, combination product, or protocol specified procedure whether investigational or marketed (including placebo, active comparator product, or run-in intervention), manufactured by, licensed by, provided by, or distributed by the Sponsor for human use in this study.

Events meeting the AE definition

- Any abnormal laboratory test results (hematology, clinical chemistry, or urinalysis) or other safety assessments (eg, ECG, radiological scans, vital signs measurements), including those that worsen from baseline, considered clinically significant in the medical and scientific judgment of the investigator.
- Exacerbation of a chronic or intermittent preexisting condition including either an increase in frequency and/or intensity of the condition.
- New conditions detected or diagnosed after study intervention administration even though it may have been present before the start of the study.
- Signs, symptoms, or the clinical sequelae of a suspected drug-drug interaction.
- Signs, symptoms, or the clinical sequelae of a suspected overdose of either study intervention or a concomitant medication.
- For all reports of overdose (whether accidental or intentional) with an associated AE, the AE term should reflect the clinical symptoms or abnormal test result. An overdose without any associated clinical symptoms or abnormal laboratory results is reported using the terminology "accidental or intentional overdose without adverse effect."
- Any new cancer or progression of existing cancer.

Events NOT meeting the AE definition

- Medical or surgical procedure (eg, endoscopy, appendectomy): the condition that leads to the procedure is the AE.
- Situations in which an untoward medical occurrence did not occur (social and/or convenience admission to a hospital).

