- Anticipated day-to-day fluctuations of preexisting disease(s) or condition(s) present or detected at the start of the study that do not worsen.
- Surgical procedure(s) planned prior to informed consent to treat a preexisting condition that has not worsened.
- Refer to Section 8.4.6 for protocol-specific exceptions.

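### The plan is unclear on whether COVID-19 is an AE; if it is, the any-AE row carries the efficacy effect and could offset about 4.6 to 6.1 points of other AEs on MOV at design efficacy

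*Combined protocol and SAP*

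**What the plan says.** Section 9.1 gives the primary safety endpoint as "Safety: AEs, and AEs leading to discontinuation of study intervention". Section 9.6.2 puts "the broad AE categories consisting of the percentage of participants with any AE, a drug-related AE, a serious AE" and related categories, including discontinuation due to an AE, in Tier 2. Table 6 gives each a between-arm difference with a 95% CI. Specific AEs, organ classes and laboratory limits reaching 1% in either arm get the same treatment. The section calls the Tier 2 intervals descriptive. No row excludes COVID-19.

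Four places bear on whether COVID-19 is an AE:

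- **10.3.1, definition.** "An AE is any untoward medical occurrence in a clinical study participant, temporally associated with the use of study intervention". The note below it extends this to any "symptom, or disease (new or exacerbated) temporally associated with the use of a study intervention".
- **10.3.1, events that are not AEs.** The list does not name COVID-19. It ends with "Refer to Section 8.4.6 for protocol-specific exceptions".
- **8.4.6.** The heading is "Disease-related Events and/or Disease-related Outcomes Not Qualifying as AEs or SAEs". The text refers to efficacy endpoints, naming hospitalizations and mortality. It says that from randomization to 14 days after the last dose "these events must be reported as described in Section 8.4.1". It relaxes reporting only after that window.
- **8.4.1.** All AEs and SAEs in that same window must be reported.

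Section 2.2.3.1 shows programme practice. In Part 1 of the outpatient treatment trial the most frequent AEs were "COVID-19 pneumonia in any MOV group and diarrhea and COVID-19 in the placebo group".

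**The concern.** In a prevention trial the disease being prevented is itself a new illness arising after randomization. If it counts as an AE, an effective drug lowers the any-AE percentage simply by working, and placebo looks worse on tolerability for a reason unrelated to tolerability. A real excess of other AEs on MOV can then be cancelled in the row that summarises the primary safety endpoint. Participants enter without symptoms and take a preventive drug, so an undistorted view of what the drug itself causes matters.

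The heading and text of 8.4.6 also disagree. One site could enter a COVID-19 episode as an AE while another, following the heading, does not. The content of a primary safety endpoint would then depend on how each site reads the section.

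**Working it through.** **1. Window.** Under 8.1.9.1 the last dose falls between Day 5 and Day 7, so AE reporting runs to about Day 19 (5 + 14) to Day 21 (7 + 14). It covers every symptom onset counted for the Day 14 endpoint.

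**2. Inputs.**
- Undetectable virus at baseline: 80% of participants; COVID-19 in 8% on placebo, 3.2% on MOV (9.9.1).
- Detectable virus at baseline: 20%; COVID-19 in 40% on placebo, 28% on MOV (9.9.2).
- Safety sample: 688 per arm, all treated participants whatever the baseline swab (9.5.2, 9.9.3).
- Background rate q of AEs other than COVID-19: not given for this trial. I assume 10% to 33%. Table 9 illustrates 10% and 20%. Part 2 of the outpatient treatment trial had any-AE rates of 30.4% and 33.0% (2.2.3.1), in people who already had COVID-19.

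**3. Reproducing the plan's own figure.** Table 8, equal allocation:
- Placebo: (550 × 0.08 + 138 × 0.40)/688 = 14.42%.
- MOV: (550 × 0.032 + 138 × 0.28)/688 = 8.17%.
- A normal approximation with pooled null variance at one-sided 0.0249 gives 95.6% power, against 95% stated.

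The rates are therefore being used as the plan uses them.

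**4. Built-in gap.**
- Placebo: 0.8 × 0.08 + 0.2 × 0.40 = 14.40%, about 99 of 688.
- MOV: 0.8 × 0.032 + 0.2 × 0.28 = 8.16%, about 56 of 688.
- Gap: 6.24 points.

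**5. Effect on the any-AE row.** Assume every case is recorded as an AE and COVID-19 is independent of other AEs. With COVID-19 rate c, any AE = 1 − (1 − q)(1 − c). The excess x of other AEs on MOV that leaves the difference at zero solves (1 − q − x)(1 − 0.0816) = (1 − q)(1 − 0.144). Hence x = (1 − q) × 0.0624/0.9184.

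| q | Any AE, placebo | Any AE, MOV, no drug effect on other AEs | Difference (points) | Excess x shown as zero (points) |
|---|---|---|---|---|
| 10% | 23.0% | 17.3% | −5.6 | 6.1 |
| 20% | 31.5% | 26.5% | −5.0 | 5.4 |
| 30% | 40.1% | 35.7% | −4.4 | 4.8 |
| 33% | 42.6% | 38.5% | −4.2 | 4.6 |

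**6. What this does to detection.** In 20,000 simulated trials with q = 20%, x = 5.4 points and 688 per arm (Wald intervals), the 95% CI indicated harm in 2.4% of trials for any AE. With COVID-19 left out it did so in about 68%.

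**7. Sensitivity.**
- 30% reduction in both strata: MOV rate 0.8 × 0.056 + 0.2 × 0.28 = 10.08%, and x = (1 − q) × 0.0432/0.8992. This is 4.3 points at q = 10% and 3.4 at q = 30%.
- No effect in the undetectable stratum: MOV rate 0.8 × 0.08 + 0.2 × 0.28 = 12.0%, and x = (1 − q) × 0.024/0.88. This is 2.5 points at q = 10% and 1.9 at q = 30%.
- Half of the cases recorded, design efficacy, q = 20%: rates 7.2% and 4.08%, and x = 0.8 × 0.0312/0.9592 = 2.6 points.

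**The case against.** The premise is an inference. No sentence says that COVID-19 is recorded as an AE, and if the 8.4.6 heading governs, the offset is close to nil. The treatment-trial tabulation is weak support, because everyone there already had COVID-19. This stands as a limit on certainty. The definition, 8.4.1 and the 8.4.6 text still favour inclusion, and the contradiction needs correcting on either reading.

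Table 6 has other views of the data. Drug-related AEs have their own row, and so does each specific AE at 1% or more. At design rates a COVID-19 term would far exceed 1%, so its contribution would be visible. Section 10.3.4 asks for the diagnosis rather than its symptoms, which helps keep the headache or nausea rows clean. A reader might infer that an excess would be wholly hidden; these rows show otherwise. The protection is partial. Drug-relatedness is investigator judgement. Appendix 2 withholds post-screening virology results from blinded sites, so some episodes may be entered as separate symptoms.

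No formal test rests on the any-AE row, and an all-cause summary is legitimate. That is a reason to keep the row, but a descriptive label does not remove the built-in difference.

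A reader might also set the masked excess against Table 9 and call the two equal. The column must match the any-AE rate, not the background rate. At q = 10% the any-AE rates are 23.0% and 17.3%, so the 20% column (6.4 points) is nearest, not the 10% column (5.0). At q = 20% they lie beyond the table. I draw no conclusion from that comparison.

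**Conclusion.** The point holds, conditionally. On the natural but inferred reading, the any-AE comparison contains the efficacy effect: 6.24 points at design rates. It could offset 4.6 to 6.1 points of other AEs on MOV, given full design efficacy in both strata, full recording, independence, and an assumed background rate of 33% to 10%. With lower efficacy or incomplete recording the figure is about 2 to 4 points.

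Two stronger readings are not supported. First, the same distortion might be inferred for the serious-AE and discontinuation rows. The serious-AE row could be affected, since 8.4.6 names hospitalizations and deaths, but the plan gives no rate of severe COVID-19 from which to size it. For discontinuation, dosing lasts 5 days, 7.1 does not list COVID-19 as a required reason to stop, and 4.1 allows COVID-19 care alongside study drug, so an effect is possible but not shown. Second, inconsistent recording between sites is a risk created by the wording; nothing in the documents shows that it happens.

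This is a cheap improvement to the safety analysis. It does not show that the safety conclusions would be wrong.

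**What to change.** 1. Make the 8.4.6 heading, its text and the 10.3.1 cross-reference agree on whether a COVID-19 episode is an AE, so that every site records it the same way.
2. In 9.6.2 and Table 6, add supplementary Tier 2 rows for any AE and any serious AE, excluding a COVID-19 term list (COVID-19, COVID-19 pneumonia and similar diagnosis terms) fixed before unblinding. Show them beside the all-inclusive rows and read the two together.

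Two further steps may be tempting and should not be taken. Removing individual symptom AEs because the participant was PCR-confirmed would condition on a post-randomization outcome that differs by arm, and would delete more genuine AEs from placebo. For the same reason, the all-inclusive rows should not be replaced as the basis of the conclusion.

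The cost is protocol and SAP wording, two table rows from data already collected, and agreement on a term list. COVID-19 episodes entered only as separate symptoms would remain in the supplementary rows, so most of the built-in effect is removed but not all of it.

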9.6.3 Demographic and Baseline Characteristics

The comparability of the intervention groups for each relevant demographic and baseline characteristic will be assessed by the use of tables. No statistical hypothesis tests will be performed on these characteristics. The number and percentage of participants screened and randomized and the primary reasons for screening failure and discontinuation will be displayed. Demographic variables, baseline characteristics, and prior and concomitant therapies will be summarized by intervention either by descriptive statistics or categorical tables.

9.7 Interim Analyses

Study enrollment is likely to be ongoing at the time of the interim analysis. Blinding to treatment assignment will be maintained at all investigational sites. The results of the interim analysis will not be shared with the investigators prior to the completion of the study. Participant-level unblinding will be restricted to an external unblinded statistician and scientific programmer performing the interim analysis, who will have no other responsibilities associated with the study.

An eDMC will serve as the primary reviewer of the interim data and will make recommendations for discontinuation of the study or protocol modifications to an executive committee of the Sponsor. If the eDMC recommends modifications to the design of the protocol or discontinuation of the study, this executive committee (and potentially other limited Sponsor personnel) may be unblinded to results at the treatment level to act on these

recommendations. The extent to which individuals are unblinded with respect to results of interim analyses will be documented. Additional details for this interim analysis and any other study data review will be provided in the eDMC Charter.

Results from the interim analysis will be provided to the eDMC by the unblinded statistician. Prior to final study unblinding, the unblinded statistician will not be involved in any discussions regarding modifications to the protocol, statistical methods, identification of protocol deviations, or data validation efforts after the interim analyses.

This study will include an interim analysis when approximately 55% (or approximately 600 across the MOV and the placebo groups) of the participants with undetectable SARS-CoV-2 in baseline NP swabs have either completed the Day 14 visit or discontinued from the study prior to the Day 14 visit. The purpose of this interim analysis is to review safety and allow for early stopping in the case of futility. There is no plan to stop the study early for efficacy. However, a small statistical penalty (α =0.0001) will be applied for this interim analysis using a Haybittle-Peto type adjustment [Haybittle, J. L. 1971] [Peto, R, et al 1976]. The final analysis will be conducted at a 0.0249 alpha-level to preserve the overall type I error level.

The allocation of the approximately 1100 participants with undetectable SARS-CoV-2 in baseline NP swabs randomized to the 2 intervention groups may not be in a 1:1 ratio, since SARS-CoV-2 in baseline NP swabs will not be available before randomization so that the number of participants in each group may vary. As an example, the case when approximately 660 participants with undetectable SARS-CoV-2 in baseline NP swabs and approximately 440 participants with undetectable SARS-CoV-2 in baseline NP swabs are randomized to MOV and placebo groups, respectively, will be discussed in this section.

The Gamma family spending function with $\gamma = -4$ will be used to set the futility boundary for the primary endpoint as a guide for the eDMC to control overall type I error rate of 0.025, one-sided. Assuming the information fraction of 55%, the nonbinding futility boundary expressed on the risk difference (MOV minus placebo) is -0.0049. The boundary crossing probabilities for futility are 59.8% under H0 and 1.4% under H1 (risk difference of -0.048). Power assessments for additional scenarios where the number of participants with undetectable SARS-CoV-2 in baseline NP swabs may be different from the scenario described above are presented in Section 9.9.1.

